9.2.3.1 Adverse Events

Adverse events for each patient will be monitored and documented from the time the subject gives informed consent at Visit 1 until the End of Study (EOS) Visit or till the rollover to the extension study, except for:

- SAEs
- AEs that are ongoing at database lock.

Adverse events, AESIs and SAEs will be reported as described in [Section 10.4](#).

9.2.3.2 Vital Signs

Vital signs blood pressure (mmHg), heart rate (beats per minute), respiratory rate (breaths per minute), body temperature (degrees Celsius), and will include height (cm) and body weight (kg), measured at the Screening and Randomization Visits (Visits 1 and 2) and every subsequent visit. Height will be measured with a proper stadiometer at every visit. Stadiometer measurements will be made without patient wearing shoes. Vital signs will be measured at clinic visits, in sitting position, using the same arm at each visit, and prior to administration of investigational product.

Refer to [Section 1.2](#) Study Flow Chart for the schedule of vital signs performed throughout this study.

9.2.3.3 ECG Variables

One recording of a standard 12-lead electrocardiogram (ECG) will be performed at Screening, EOT, and EOS (see [Section 1.2](#)).

9.2.3.4 Physical Examination

Physical examinations will include an assessment of general appearance, skin, eyes, ear/nose/throat, heart, chest, abdomen, reflexes, lymph nodes, spine, and extremities, including menstruation status ([Section 7.2.3](#)). All deviations from normal will be recorded, including those attributable to the patient's disease. Refer to [Section 1.2](#) Study Flow Chart for the schedule of physical examination performed throughout this study.

9.2.3.5 Clinical Laboratory Safety Variables

The clinical laboratory tests will be conducted by an accredited (College of American Pathologists or equivalent) central laboratory with national and regional clinical licenses as required for diagnostic testing and must provide evidence of participation in proficiency testing, as appropriate. After reviewing the laboratory report and evaluating any results that are outside the normal range, the Investigator must sign and date the laboratory report.

Abnormal laboratory values that are considered to be clinically significant by the Investigator should be repeated as soon as possible after receiving the laboratory report to rule out laboratory error. Persistent abnormal laboratory values should be repeated until they return to normal or until an etiology of the persistent abnormality is determined.

Refer to [Section 1.2](#) Study Flow Chart for the description of the clinical laboratory evaluations and the schedule of laboratory evaluations performed throughout this study.

The clinical laboratory parameters that will be measured in safety hematology and chemistry blood samples are:

- Hematology: To include hemoglobin, hematocrit, platelet count, total white blood cell count with five-part differential count, and total red blood cell count.
- Serum chemistry: To include: creatinine, blood urea nitrogen, glucose, uric acid, total cholesterol, total protein, albumin, total bilirubin (in case of values above the normal range, differentiation in conjugated and non-conjugated bilirubin), ALT, AST, alkaline phosphatase (ALP), lactate dehydrogenase, electrolytes (sodium, potassium, chloride), bicarbonate, and CPK. Patients' fasting or non-fasting status at blood sample collection will be recorded on the Central Laboratory Requisition Form. Fasting is considered as no intake of food or any drink except for water for at least 8 hours.
- Urine dipstick analysis including specific gravity, pH, glucose, ketones, blood, protein, nitrate, leukocyte esterase, urobilinogen and bilirubin (by dipstick). If any parameter on the dipstick is abnormal, a urine sample should be sent to the central laboratory for testing. If positive for proteins, microscopic analysis is performed by central laboratory.
- Clinical laboratory testing at Screening Visit 1 will include HBs-Ag, hepatitis B surface antibody (HBs-Ab), HBc-Ab, HCV-Ab, HIV screen (Anti-HIV-1 and HIV-2 antibodies) and anti-nuclear antibody (ANA).

Table 1 - Eligibility interpretation for hepatitis serology

Hepatitis Serology Result	Protocol Action
HBs Ag positive or indeterminate	Excluded
HBs Ab positive, HBs Ag negative, HBc Ab negative	Eligible
IgM HBc Ab positive	Excluded
Total-HBc Ab positive (with or without HBs Ab positive)	Test for HBV DNA 
 • If HBV DNA positive: excluded • If HBV DNA negative/not detected^a: eligible
HCV antibody positive	Test for HCV RNA 
 • If HCV RNA positive: excluded • If HCV RNA negative/not detected: eligible

^a It is recommended that patients who are receiving potentially immunosuppressive therapy and are IgG HBcAb positive and HBV DNA negative undergo surveillance HBV DNA studies every 1-3 months depending upon the individual potential therapeutic risk and comorbidities. If necessary, a hepatologist should be consulted on a case-by-case basis.
HBc Ab: Hepatitis B core antibody; HBs Ab: Hepatitis B surface antibody; HBs Ag: Hepatitis B surface antigen; HBV DNA: Hepatitis B virus DNA; HCV RNA: Hepatitis C virus RNA.

Decision trees for the management of certain laboratory abnormalities by Sanofi are provided in [Appendix K](#).

9.2.3.6 Other Safety Laboratory Tests

9.2.3.6.1 Serum Immunoglobulins and Subtypes

Serum immunoglobulins: quantitative immunoassays for total IgG, IgG subclasses 1–4, IgM, and IgA.

Please note that Total IgE, antigen-specific IgE, and antigen-specific IgG4 are assessed as pharmacodynamic parameters (eg, to determine the change from Baseline in IgE/IgG4 ratio; see [Section 9.4.2](#)).

As a precaution for maintenance of treatment blinding, results for immunoglobulins will not be released to Investigators during the study, unless required for investigation of other safety findings in individual patients.

9.2.3.7 Pregnancy Test

A urine pregnancy test will be performed at Screening (Visit 1) in female patients of childbearing potential who have commenced menstruating, and a urine dipstick pregnancy test will be performed at Visit 2 prior to randomization and other clinic visits prior to administration of IMP. A negative result must be obtained at Visit 1 and 2 prior to randomization. Refer to [Section 1.2](#) Study Flow Chart for the schedule of pregnancy tests performed throughout this study. Those female patients who commence initial menstruation during the study will be similarly monitored with urine dipstick pregnancy tests and contraception consulting for the duration of the study.

9.3 OTHER SECONDARY ENDPOINTS

9.3.1 Systemic Drug Concentration, Anti-drug Antibodies, and IgG responses to vaccination during drug treatment

- Serum functional dupilumab concentrations
- ADA
- IgG responses to vaccination with any vaccination for tetanus, diphtheria, pertussis and/or seasonal trivalent/quadrivalent influenza vaccine during dupilumab treatment (may be analyzed as exploratory endpoint if insufficient power).

9.3.1.1 Systemic Drug Concentration and Anti-drug Antibodies

9.3.1.1.1 Sampling Time

Predose blood samples will be collected for determination of functional dupilumab concentration in serum and anti-dupilumab antibodies (including neutralizing antibodies) on days designated in the Study Flow Chart (see [Section 1.2](#) as well as [Section 10.3.4](#), as needed for Brazil). The date of collection should be recorded in the patient e-CRF. The date and time also will be collected on the central laboratory requisition form and entered into the database through data transfers from the central laboratory.

If an SAE or AESI occurs in a patient, blood samples should be collected for determination of functional dupilumab concentration, and anti-dupilumab antibody assessment at or near the onset and completion of the occurrence of the event, if possible. The exact date and time of sample collection must be recorded and entered into the database by the central laboratory. An unscheduled systemic drug concentration page in the e-CRF must be completed as well.

Further follow-up of individual patients will be considered based on the overall assessment of antibody titers and clinical presentation.

9.3.1.1.2 Handling Procedures

Special procedures for collection, storage, and shipping of serum are described in separate operational manuals. An overview of handling procedure for samples used in the determination of systemic drug concentration and anti-drug antibodies is provided in [Table 2](#).

Table 2 - Summary of handling procedures for dupilumab

Sample type	Functional dupilumab	Anti-dupilumab antibody
Matrix	Serum	Serum
Blood sample volume	2 mL	2 mL
Anticoagulant	None	None
Blood handling procedures	See Operational Manual	See Operational Manual
Serum aliquot split	Two aliquots	Two aliquots
Storage conditions	<6 months: below -20°C <24 months: below -80°C (preferred)	<6 months: below -20°C <24 months: below -80°C (preferred)
Serum shipment condition	In dry ice	In dry ice

9.3.1.1.3 Bioanalytic Method

Serum samples will be assayed using validated methods as described in [Table 3](#).

Table 3 - Summary of bioanalytical methods for dupilumab and anti-dupilumab antibody

Analyte	Functional dupilumab	Anti-dupilumab antibody
Matrix	Serum	Serum
Analytical technique	ELISA	Electrochemiluminescence
Site of bioanalysis	Regeneron	Regeneron

ELISA: enzyme-linked immunosorbent assay

9.3.1.2 Humoral Immune Response to Vaccines

Humoral immune responses to standard vaccines (in this study: any vaccination for tetanus, diphtheria, pertussis and/or seasonal trivalent/quadrivalent influenza vaccine) occurring during dupilumab treatment will be evaluated for those patients eligible for these vaccinations.

At Screening, parent(s)/caregiver(s)/legal guardian(s) will be asked to provide information on their child's vaccination record and schedule, and assess whether immunizing their children with any vaccination for tetanus, diphtheria, pertussis and/or seasonal trivalent/quadrivalent influenza (as per local medical practice) will result in vaccination during the study.

Any patient who will receive planned vaccination for tetanus, diphtheria, pertussis and/or seasonal trivalent/quadrivalent influenza during the study, will be scheduled to receive the respective vaccination(s) and to have blood samples for antibody titers drawn before and after the respective vaccination(s), as detailed below, and as shown in the Study Flow Chart ([Section 1.2](#)).

Scheduled blood sample collection for pre- and post-vaccine antibody titers, for both vaccinations (ie, any tetanus, diphtheria and pertussis and/or seasonal trivalent/quadrivalent influenza) should be drawn within 8 weeks prior to vaccination and at 3-4 weeks (up to 6 weeks) after the respective vaccination(s); however, all blood titer samples must be drawn between Week 6 and Week 50 (ie, Visit 5 and Visit 27, respectively).

Depending on patient's vaccination schedule during the course of this study, every effort should be made to draw pre-vaccination titers at either Weeks 6, 12, or 24 (V5, V8, V14) of the Randomized Treatment Period, and to draw post-vaccination titers at either Weeks 12, 24, 36 or 50 (V8, V14, V20, V27) of the Randomized Treatment Period (see Study Flow Chart [Section 1.2](#)).

For patient(s) requiring urgent/emergency vaccination with any seasonal trivalent/quadrivalent influenza and/or any tetanus, diphtheria and pertussis vaccine (eg, flu season approaching, animal bite, emergency room standard procedures, etc) between Week 6 and Week 44 (ie, Visit 5 and Visit 24, respectively), the actual vaccination(s) may be given by physicians or qualified caregivers outside the study clinic; however, every effort should be made to obtain blood samples for pre- and post-vaccine antibody titers at scheduled draws as described above. Should vaccination be unable to be planned in accordance with other study blood draws (eg, tetanus vaccination for accidental puncture wounds, etc) as outlined above, at the discretion of the Investigator and with agreement of patient parents or caregiver, additional blood draws may be performed to obtain pre-vaccination and post-vaccination titers.

9.3.1.3 Biomarker endpoints

- Change from baseline in fractional exhaled nitric oxide (FeNO) at Week 12.

Fractional exhaled nitric oxide (FeNO) will be analyzed using a NIOX instrument (Aerocrine AB, Solna, Sweden), or similar analyzer using a flow rate of 50 mL/s, and reported in parts per billion (ppb). This assessment should be conducted prior to spirometry and following a fast of at least 1 hour. Further details on the procedure for measuring exhaled nitric oxide with NIOX will be provided in a separate instruction manual.

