Clinical trial summary 11.4.2.3 Multiplicity considerations	To specify that different hierarchy orders are to be used for US and US reference countries and EU and EU reference countries.	
Clinical trial summary 8.4 Method of assigning patients to treatment group 11.1 Determination of sample size	Removal of the limit in enrolling patients according to background therapy with medium-dose ICS or blood eosinophil count level	

Section # and Name	Description of Change	Brief Rationale
Clinical trial summary	To describe the Planned Database lock	To define a date for database lock when all randomized patients complete the week 52 visit or discontinue from the study before week 52.
Clinical trial summary 9.3.1.3 Biomarker endpoints 9.4.1 Exploratory endpoints	To classify FeNO as a secondary endpoint instead of an exploratory endpoint.	Based on the strong pharmacodynamics effect of FeNO on QUEST, the Sponsor anticipates similar effect in this population and feels appropriate to investigate it as secondary endpoint.
1.2 Study flow chart footnote y 9.2.3.5 Clinical Laboratory Safety Variables	To describe the fasting status	Fasting status will be described as no intake of any food or drink except for water for at least 8 hours.
1.2 Study Flow Chart; footnote m 8.1.4 Dosing schedule	To allow for home dosing start after Visit 9	IMP home administration is allowed at any visit following Visit 9 after parents have been trained and PI has allowed.
Clinical trial summary 7.1 Inclusion Criteria	To clarify that ACQ 5 data collected on V2 can be used for inclusion criterion 01	To clarify that ACQ 5 value at V2 shall be considered for the evidence of uncontrolled asthma described in inclusion criterion 01
9.2.2.4.1.1 ACQ-7-IA (Asthma Control Questionnaire–Interviewer Administered, 7-question version)	To clarify how ACQ-7 value is calculated for statistical analysis	To add the information that for statistical analysis, ACQ-7 global score is calculated by sponsor using the BMS post central reading value for %predicted FEV1 for the question 7 of the questionnaire.
██████████ ██████████ ██████	██████████ ██████████	██ ██ ██████████
10.3.5 Procedure and Consequence for Patient Withdrawal from Study	To remove a sentence on the possible hurdle to public health value of the study in case of study withdrawal	To remove the sentence due to the change in Protocol template

CLINICAL TRIAL SUMMARY

COMPOUND: Dupilumab	STUDY No.: EFC14153

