11.4.2.2.3 Analysis of Change from Baseline for Other Continuous Variables

The change from baseline for other continuous endpoints will be analyzed using MMRM in the same fashion as for the endpoint of pre-bronchodilator % predicted FEV1. The covariates to be included are treatment, age, weight (≤ 30 kg, > 30 kg), region, baseline eosinophil (< 300 cells/ μ L, ≥ 300 cells/ μ L), baseline FeNO level (< 20 ppb, ≥ 20 ppb), baseline ICS dose level (medium/high), visit, treatment-by-visit interaction, corresponding baseline value and baseline-by-visit interaction. Sex and height will be included as covariates in the models, if the endpoint belongs to spirometry parameters. Descriptive statistics including number of patients, mean, standard error and LS means will be provided for each timepoint. In addition, differences in LS means, the corresponding 95% CI and the p-value will be derived from the MMRM model for comparison of dupilumab against placebo at each timepoint.

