compares the change from baseline in % predicted pre-BD FEV1 for the patients randomized to the dupilumab and placebo arms, regardless of what treatment patients actually received. It assesses the benefits of the treatment policy or strategy relative to placebo.

An unstructured correlation matrix will be used to model the within-patient errors. Parameters will be estimated using restricted maximum likelihood method with the Newton-Raphson algorithm. Statistical inferences on treatment comparisons for the change from baseline in % predicted FEV1 at Week 12 will be derived from the mixed-effect model. Difference in LS mean change from baseline, the corresponding 95% CI and the p-value with Kenward-Roger adjustment will be provided for comparison for dupilumab against placebo. In addition, descriptive statistics including number of patients, mean, standard error and LS mean of change from baseline will be provided.

A sample SAS code can be found below:

```
proc mixed data=adsd.adre method=reml;

    where paramcd='FEV1PP' and ATPT='PRE-BRONCHODILATOR' and avisitn ge 3 and
    avisitn le 8 and ittfl='Y';

    class subjid weight eosblgpn1 fenoblgn1 ics trt01pn avisitn cntygr1n ethnicity;

    model chg = trt01pn weight ics eosblgpn1 fenoblgn1 cntygr1n ethnicity avisitn
    trt01pn*avisitn base base*avisitn/ddfm=kr residual;

    repeated avisitn/type=un subject=subjid;

    lsmeans trt01pn*avisitn /pdiff cl;

    estimate 'dupilumab vs Placebo at Week 12 Visit 8'

    trt01pn -1 1 trt01pn*avisitn 0 0 0 0 0 -1 0 0 0 0 0 1/cl;

run;
```

The primary estimand for the key secondary endpoint is summarized as in below [Table 7](#).

Table 7 - Summary of primary estimand for key secondary endpoint

Endpoint Category (estimand)	Estimands			
	Endpoint	Population	Intercurrent event(s) strategy and missing data handling	Population-level summary
Primary objective: The primary objective is to evaluate the efficacy of dupilumab in children 6 to <12 years of age with uncontrolled persistent asthma				

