2.4.4.3 Analyses of secondary efficacy endpoints

2.4.4.3.1 Change from baseline for continuous endpoints

Change from baseline in ACQ-7-IA Week 24 will be analyzed using MMRM model including change from baseline up to Week 24 as response variables, regardless if the patient is on treatment or not when the endpoint is measured. Change from baseline in FeNO at Week 12 will be analyzed using MMRM including change from baseline up to Week 12 as response variables, regardless if the patient is on treatment or not when the endpoint is measured. The analyses for the secondary endpoints of ACQ-7-IA and FeNO will be performed in the Type 2 inflammatory

asthma phenotype, baseline blood eosinophils ≥ 0.3 Giga/L, baseline blood eosinophils ≥ 0.15 Giga/L, baseline FeNO ≥ 20 ppb and full ITT populations. When performing these analyses in the Type 2 inflammatory asthma phenotype, baseline blood eosinophils ≥ 0.15 Giga/L or full ITT population, the MMRM models will include treatment, age, baseline weight, region (pooled country), baseline eosinophil level, baseline FeNO level, baseline ICS dose level, visit, treatment by-visit interaction, baseline endpoint value, and baseline-by-visit interaction as covariates. When performing these analyses in the baseline blood eosinophils ≥ 0.3 Giga/L population, the baseline eosinophil level will be removed from the model covariates. When performing these analyses in the baseline FeNO ≥ 20 ppb population, the baseline FeNO level will be removed from the model covariates. An MMRM model including measurements up to Week 52 will also be used to derive LS mean change at all time-points in the Type 2 inflammatory asthma phenotype and baseline blood eosinophils ≥ 0.3 Giga/L populations, with including the same set of model covariates as specified for the secondary endpoint analyses. Differences in LS means, the corresponding 95% CI and the p-value will be provided for comparison between dupilumab and placebo along with descriptive statistics.

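### The FeNO Week 12 model, read naturally, shares one covariance across arms; if dupilumab lowers FeNO roughly proportionally, its ppb confidence intervals will be somewhat too narrow (minor)

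*Protocol*

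**What the plan says.** Protocol 9.3.1.3 defines the endpoint as "Change from baseline in fractional exhaled nitric oxide (FeNO) at Week 12", measured in ppb. The amendment summary table explains its move from exploratory to secondary: "Based on the strong pharmacodynamics effect of FeNO on QUEST", the sponsor expects a similar effect in this population.

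The analysis is in SAP 2.4.4.3.1: "Change from baseline in FeNO at Week 12 will be analyzed using MMRM including change from baseline up to Week 12 as response variables". The model adjusts for, among other terms, "baseline endpoint value, and baseline-by-visit interaction as covariates". It has no treatment-by-baseline term, log transform or robust standard error, and that paragraph names no covariance structure.

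The structure has to be carried over from elsewhere. Protocol 11.4.2.2.3 says: "The change from baseline for other continuous endpoints will be analyzed using MMRM in the same fashion as for the endpoint of" pre-bronchodilator % predicted FEV1. SAP 2.4.4.2.1 specifies an unstructured matrix for FEV1, and its sample code reads "repeated avisitn/type=un subject=subjid". There is no GROUP option, so both arms share one covariance.

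FeNO at Week 12 occupies tests 20 to 24 in both hierarchies (SAP 2.4.4.4, Tables 9 and 10). Differences in LS means are to be reported with 95% confidence intervals.

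**The concern.** FeNO cannot be negative and is usually skewed. If a drug multiplies it by a constant below 1, the residual spread around the baseline regression is multiplied by the same constant, but only in the treated arm. Allocation is 2:1 to dupilumab, so a pooled variance is weighted towards the larger, less variable arm. The variance of the treatment difference, however, is driven mainly by the smaller, more variable placebo arm. The model standard error is then too small. The Kenward-Roger adjustment corrects for small samples; it does not repair a covariance wrongly shared between arms.

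What is at stake is the width of the reported FeNO intervals. The shortfall is largest when the drug acts strongly, which is the case the sponsor expects to report.

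**Working it through.** **Inputs from the documents.** 402 patients, 268 dupilumab and 134 placebo (Protocol, Clinical Trial Summary and 11.1); about 345 type 2 patients and about 255 with eosinophils ≥0.3 Giga/L (SAP 1.1). The plan's figures reproduce: 402 × 2/3 = 268; 0.86 × 402 = 345.7; 0.64 × 402 = 257.3. No FeNO mean, SD, percent suppression or arm-specific variance is given, so everything below on FeNO is assumed.

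**Closed form.** Let r be the ratio of baseline-adjusted residual SDs, dupilumab over placebo, with the placebo SD set to 1.

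- Pooled variance ≈ (2r² + 1)/3, so SE²(model) = (2r² + 1)/3 × (1/268 + 1/134) = (2r² + 1)/268.
- SE²(true) = r²/268 + 1/134 = (r² + 2)/268.
- Ratio q = √[(2r² + 1)/(r² + 2)]; coverage = 2Φ(1.96q) − 1.

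Example, r = 0.5: q = √(1.5/2.25) = 0.816 and coverage is 89.0%.

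| r | q | Coverage |
|---|---|---|
| 0.25 | 0.738 | 85.2% |
| 0.4 | 0.781 | 87.4% |
| 0.5 | 0.816 | 89.0% |
| 0.6 | 0.853 | 90.6% |
| 0.7 | 0.891 | 91.9% |
| 0.9 | 0.966 | 94.2% |
| 1.0 | 1.000 | 95.0% |
| 1.25 | 1.076 | 96.5% |

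Coverage of 85% to 93% corresponds to r of about 0.24 to 0.79.

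**What r would be.** Under uniform suppression by a fraction d, r is about 1 − d. A simulation of lognormal FeNO at 230:115 (345 split 2:1; Week 12 ANCOVA on ppb change, adjusted for baseline FeNO and the 20 ppb category; 3,000 replicates per scenario) confirms this:

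| Uniform suppression | r | Coverage, shared variance |
|---|---|---|
| None | – | 95.0-95.4% |
| 30% | about 0.7 | 91.2-92.9% |
| 40% | about 0.6 | 90.0-90.8% |
| 50% | 0.5 | 87.8-89.1% |
| 60% | about 0.4 | 86.9-87.7% |

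The SD of the raw change hardly narrows in these scenarios (ratio about 0.85-1.03, including 70% suppression). A table of raw change SDs by arm would therefore not reveal the problem.

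**Adding variation in response between children.** With response log-SD 0.5, the same simulation gives r about 1.0 and coverage 95.4% at 30% suppression, 92.0% at 50% and 89.4% at 60%. At 30% the shortfall has gone.

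**Effect of the remedies.** A second set of 1,500 trials per scenario assumed median baseline 20 ppb, log SD 0.8, SD of log change 0.35-0.5 and 15% regression to the mean. The robust standard error is HC3.

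| Scenario | Shared variance | Robust SE | Log scale |
|---|---|---|---|
| Uniform 30% | 91-93% | 94% | 94-95% |
| Uniform 50% | 88-89% | 94-95% | 95-96% |
| Uniform 60% | 87% | 93% | 94-95% |
| 50%, response log-SD 0.3 | 90-91% | 93% | 97% |
| 60%, response log-SD 0.3 | 88% | 94% | 96% |
| 60%, response log-SD 0.5 | 91-92% | 94% | 97-98% |

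Over all runs, including a 255-patient subset, shared-variance coverage was about 85-93% under uniform 30-60% suppression and about 86-97% with varying response. Arm-specific or robust standard errors gave about 90-96%. All of this is complete-data, single-visit ANCOVA, which approximates the Week 12 contrast of the MMRM.

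**The case against.** **The coverage figure is not in the plan.** A reader might infer that the FeNO intervals will cover 85-93% as a fact. The documents do not support that. They call the effect strong but give no size, and Protocol 9.4.2 says that children may differ from adults in their biomarker profile. With variable response and modest suppression, r reaches 1 or more (about 1.0 in one simulation, about 1.3 in another) and the interval is not too narrow. This objection stands, and the size has to be stated as conditional.

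**The shared covariance is inferred.** It is explicit only for % predicted FEV1. This also stands, but no other structure is offered and the protocol's cross-reference points to the FEV1 model.

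**Relative effect is already described.** SAP 2.4.6.2 summarises absolute and percent change in each biomarker by arm and time point, and FeNO change is analysed separately in children with baseline FeNO ≥20 ppb (test 23). This answers much of the worry that one ppb figure fits neither high- nor low-FeNO children. It does not correct the width of the tested intervals.

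**Moving the test to the log scale is not a neutral repair.** It replaces the protocol's ppb change with a ratio of geometric means. Its good coverage here is also partly circular, because the data were simulated as lognormal, and it over-covers (97-98%) in some variable-response scenarios. This stands, so the log ratio belongs in a supportive analysis.

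**No conclusion changes.** FeNO tests come last and are reached only if the 19 earlier tests succeed. This limits the severity.

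**Conclusion.** The point holds as a conditional, minor one. The SAP leaves the FeNO error structure to be inherited from FEV1, and the inherited structure understates the standard error whenever the residual spread is smaller on dupilumab. That is the expected direction if suppression is strong and roughly proportional. The size depends on FeNO assumptions that the documents do not supply and runs from a material shortfall (about 85% coverage) to none.

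A reader might also infer that false-positive FeNO claims become more likely. They do not: with no drug effect on FeNO the arms have equal spread, and coverage is 95%. Primary and key secondary inferences are untouched. The harm is confined to overstated precision in the FeNO intervals of tests 20 to 24.

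**What to change.** In SAP 2.4.4.3.1, state that the FeNO MMRM uses a treatment-specific unstructured covariance (`group=trt01pn` in the REPEATED statement). If that model does not converge, use an empirical (sandwich) standard error and name the degrees-of-freedom method that goes with it. Keep the ppb change as the tested endpoint. Add a supportive analysis of log(Week 12/baseline) with log baseline FeNO as covariate, reported as a percent difference.

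Cost: SAP wording, a code option and one extra output. The ppb intervals become somewhat wider. With six post-baseline visits to Week 12, covariance parameters rise from 6 × 7/2 = 21 to 42, which is why the fallback is needed. Coverage improves to about 90-96% in the scenarios run, but not always fully to nominal.
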